### **4.3 Intervention**

The intervention in our study will allow us to determine which approach to the management of patient-reported symptom data is most effective from a patient and caregiver perspective. In both groups, if a patient reports severe symptoms, they are instructed to immediately contact their physician's office or seek medical attention.

#### **Cohort 1: Team Monitoring**

Team Monitoring is the current standard of care for patients at JRSC. In this cohort, the electronic system will provide advanced informatics support for push notifications to the care team based on the severity of the symptoms reported. This platform promotes early detection and intervention. The care team is alerted when patients experience symptoms out of the expected range or if symptoms are worsening. Nurses receive secure message notifications and will contact the patient by phone depending on symptom severity. If a patient responds with a moderate-severe answer, the office team gets an alert and calls

the patient during business hours. Although nurses endeavor to call patients within 24 hours, this may not occur if symptoms are reported on weekends or holidays. If the patient reports very severe symptoms, they get a bold red alert instructing them to call the office (or call team after hours) immediately or seek medical attention. The actual response thresholds (i.e., when to give which alert) for each question are set individually and have been refined based on feedback from the office practice nurses. The workflow associated with Team Monitoring has been vetted by all teams at JRSC and has been operationalized for urology, breast, and gynecologic oncology patients.

## **Cohort 2: Enhanced Feedback**

In this cohort, the electronic system will provide tailored normative data visualizations that offer context and education to patients regarding expected symptom severity. The information provided to patients in the Enhanced Feedback group will be procedure specific and based on continuously updated PRO-CTCAE data from previous patients. Patients are thus able to see their own recovery trajectory relative to that of patients who have undergone the same procedure. Care is patient-activated in that patients will use the information about expected symptoms to decide whether they should call the care team (e.g., if they are experiencing symptoms that are more severe or more prolonged than expected). If a patient reports severe symptoms, they are instructed to immediately contact their physician's office or seek medical attention. In addition, when patients in the Enhanced Feedback group report severe symptoms, the care team will receive an alert but as noted above, alerts to the clinical team can only be monitored during business hours, so all patients must seek care after hours in the current standard care fashion.

## **The JRSC Recovery Tracker Platform**

As the current standard of care, patients undergoing surgery at JRSC are asked to report on 11 items from a validated instrument, the Patient Reported Outcomes Common Terminology Criteria for Adverse Events (PRO-CTCAE), three additional surgical symptom questions, and two questions about seeking urgent care or a doctor during the first 10 days after surgery. Over the following 20 days, patients can tailor the survey to their needs by choosing when they complete the survey. Between days 11-30, patients can report symptoms on any day. By leaving the survey open after day 10, patients who develop new or worsening symptoms will have the ability to report these symptoms electronically whenever they wish. Conversely, patients not experiencing any symptoms will not be burdened by additional surveys. This system is currently being further refined within the JRSC PRO Workgroup.

Invitations to complete questionnaires are triggered automatically on the basis of visit and operative schedules and sent via secure message to patients through the Patient Portal. The interface is built with a responsive design, so participants have the option of using the system via computers, tablets, or smart phones. Questionnaires are available in both English and Spanish. Nurses receive secure message notifications when patients' symptoms exceed expected values or worsen and will contact the patient by phone within 24 hours, depending on symptom severity. Patient symptom responses integrate directly into our electronic health record in two ways: (1) into nursing documentation templates

for point-of-care verification and (2) into the electronic health record reports after review of the data by the care team.

### The PRO-CTCAE symptom questions

The JRSC platform is based on the PRO-CTCAE symptom questions. In cancer clinical trials, adverse events are collected and reported using the National Cancer Institute's CTCAE. To improve precision and patient-centeredness in the capture of symptomatic adverse events, the NCI funded a team of investigators led by [name] to develop a library of PRO items to supplement the CTCAE, called the PRO-CTCAE. Of the 790 adverse events in the CTCAE, 78 were identified as amenable to patient self-report. For each of these adverse events, PRO items were created reflecting the attributes of presence, frequency, severity, interference with usual or daily activities, and/or amount. One to three attributes were selected for any given adverse event, depending on the nature of that particular adverse event. In total, 124 individual items represent the 78 symptomatic adverse events in the PRO-CTCAE item library. Each item includes a plain-language term for the adverse event, the attribute of interest, and the standard recall period of "the past 7 days" (in the current study, we plan to use a 1-day recall period since patients are asked to report daily). Cognitive interviews previously determined a high level of patient understanding and meaningfulness of the items, and a national multisite validation study led by [name] showed that items were valid, reliable, and sensitive to change. Additional development work by the team of Drs. [name] and [name] included testing administration mode equivalence, relationship among various recall periods, and a Spanish translation. PRO-CTCAE items were selected for the symptom monitoring system and are now a component of routine clinical care for MSKCC patients undergoing surgery at JRSC. Eleven PRO-CTCAE items, plus 9 additional questions that were specifically targeted to capture important post-operative problems, evaluate the symptoms of patients recovering from ambulatory surgery in the MyMSK Patient Portal. Patients, nurses, surgeons, and anesthesiologists participated in the selection of these items. The items assess symptoms such as pain, nausea, fatigue, constipation, vomiting, fever, chills, dyspnea, swelling, discharge, and redness.

### Study outcomes

	Aims	Measure	Data Source(s)	Assessment Time Point
Patient-Centered Outcomes	SA1			
Emergency Department Visits	SA1a	UCC visit at MSKCC	MSK institutional database	Up to 30 days after surgery
	SA1a	Emergency department visit outside MSKCC	Patient self-reporting via Patient Portal and corroborating phone call to patient by study team; MSK institutional database	Up to 30 days after surgery
Readmissions	SA1a	Readmission to MSK	MSK institutional database	Up to 30 days after surgery
	SA1a	Admission outside MSK	Patient self-reporting via Patient Portal and corroborating phone call to patient by study team; MSK institutional database	Up to 30 days after surgery
Symptom-Triggered Interventions	SA1b	Nurse calls due to alerts	Documented in EMR via clinical information system	Up to 30 days after surgery
	SA1b	Unplanned clinic visits and phone referral to clinic	Documented in EMR	Up to 30 days after surgery

	SA1b	Pain management referrals	Documented in EMR	Up to 30 days after surgery
	SA1b	Adverse event detection	EMR and MSKCC Surgical Secondary Events Database	Up to 30 days after surgery
Patient and Caregiver Health Care Experience	SA2			
Patient Engagement	SA2a	The Patient Activation Measure 	Patient self-report	Preoperatively (day of consent-POD1), 2 weeks (+7/-3 days), 60 (+/- 14) days after surgery
	SA2a	Qualitative data	Semistructured patient interviews	30 (+/- 10) days after surgery
Patient Anxiety	SA2b	PRO-CTCAE Anxiety Items	Patient self-report via symptom monitoring module in the Patient Portal	Daily for 10 days after surgery
Caregiver Burden	SA2c	Caregiver Reaction Assessment 	Caregiver self-report	2 weeks (+7/-3 days), 60 (+/- 14) days after surgery
	SA2c	Qualitative data	Semistructured caregiver interviews	30 (+/- 10) days after surgery

### Patient-centered outcomes

We will evaluate the frequency of urgent care center (UCC) visits, readmissions and symptom-triggered interventions (pain management referrals, nursing calls) through triggers generated from the informatics platform as well as through thorough chart extraction by the clinical research coordinator (CRC) for 30 days after surgery.

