### **Data sources and data linkage plans**

Many of the study endpoints will be obtained from MSKCC's institutional database. Endpoints such as MSKCC emergency department visits, nursing follow-up calls, clinic visits, and intrainstitutional referrals are automatically captured as part of electronic medical record (EMR)-enabled care management. Emergency department visits at outside institutions will be captured by a question on our daily symptom surveys and routine follow-up surveys. Responses to the follow up surveys will be captured electronically via MSK Engage. Patients describing an emergency department visit at an institution other than MSKCC are contacted by clinical staff for further details as a routine part of follow-up care. Adverse events are captured by the MSKCC Secondary Surgical Event database. Outside emergency department visits and admissions for patients participating in MSKCC's electronic health information exchange will also be utilized. Electronic health information exchange is carried out through organizations known as Health Information Exchanges (HIEs) or Regional Health Information Organizations (RHIOs). This data is captured within MSKCC's institutional database. Data for all patients who choose to opt out of the health information exchange program will not be used. To note: MSK may join additional HIEs or RHIOs in the future. Any available HIE or RHIO data for participating patients will be collected. PROs are obtained through MSKCC's symptom monitoring software, the same software used to implement symptom self-reporting. Covariates such as age, sex, and race are routinely captured in the MSKCC EMR. Comorbidities are captured by an MSKCC platform used to take the baseline medical history in all surgical patients potentially eligible for ambulatory cancer surgery. Caregivers' responses to the Caregiver Reaction Assessment questionnaires will be

collected via REDCap, a secure web application for building and managing online surveys and databases. In the event the REDCap survey is unavailable, a hardcopy form will be provided to caregivers to complete.

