### **Reporting plan with assessments of internal and external validity**

This is a randomized trial with good allocation concealment, and therefore selection bias can be discounted. Patients, however, will not be blinded. This is not an important issue for the primary endpoint, which is emergency department visits, as this is objectively measured and not susceptible to reporting bias. The question of performance bias in terms of differential patient behavior is complicated by the fact that the *aim* of the trial is to change behavior. Performance bias by clinicians is, however, a concern. For instance, it is plausible that a nurse speaking to a study patient by phone in the days after discharge might make differential recommendations about the necessity of an emergency department visit depending on patient assignment. However, this is an unlikely scenario given the context of nursing care at MSKCC. Nurses call large numbers of patients, both those eligible for the trial (ambulatory care surgery) and those ineligible (e.g., complex operations requiring an in-patient stay), and they are unlikely to know which patients are and are not on trial. Patients might potentially reveal allocation to nurses during the phone call (e.g., “I saw on the website that...”). But, again, as a large number of nurses will be dealing with a large volume of patient calls, it is unlikely that allocation will bias the advice given to a significant extent.

Regarding external validity, the system is currently in use by MSKCC patients, but it is possible that these patients (a referral population in a major urban center) may have higher computer literacy, health literacy, or numeracy than the general population. We recognize that usability barriers that might seem trivial to a highly technology-focused audience can sometimes seem insurmountable for patients facing stress due to illness or treatment or for patients who face preexisting hurdles in terms of computer literacy, health literacy, or numeracy. As a result, we have built in a brief user-centered design stage supervised by coinvestigator [name] to review the existing platform in a systematic fashion, elicit constructive feedback from representative users, and perform rapid-cycle modifications to ensure usability and utility for users. We anticipate that this intensive user-centered design project will successfully adapt the existing instrument.

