### **12.3 Randomization**

At the time of protocol consent, it will be explained to patients that they will be completing symptom self-reported questionnaires for up to 30 days after surgery (daily for postoperative days 1 to 10 and then at tailored time points) as a component of routine care, and they will be asked whether they are willing to be randomized to potentially receive additional information that may help them interpret the severity of their symptoms. Randomization will be implemented through CRDB, a fully secure, password-protected database that ensures full allocation concealment. It will be performed within 1 week of the patients' surgical visit. Randomization will be stratified by procedure and will be implemented by randomly permuted blocks of random length. The trial will not be blinded, as it relies on patient knowledge (i.e., how a patient's scores compare with other patients' scores) as a key part of the intervention.

Stratification will be based the following surgical procedure types:

- Gynecologic
  - Laparoscopic or robotic procedure
  - Laparotomy
  - Other
- Breast/Plastics
  - Mastectomy alone (with or without sentinel node and axillary node dissection)
  - Lumpectomy (with or without sentinel node and axillary node dissection)
  - Tissue expander placement
  - Other
- Urology
  - Prostatectomy laparoscopic or robotic
  - Partial or total nephrectomy- laparoscopic or robotic
  - Laparotomy
  - Other
- Head and Neck
  - Thyroidectomy
  - Other

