### 13.1 DATA MANAGEMENT ISSUES

A Clinical Research Coordinator (CRC) and a Research Project Manager (RPM) will be assigned to the study. The responsibilities of the CRC and RPM include project compliance, data reporting, regulatory monitoring, problem resolution and prioritization, and coordinating the activities of the protocol study team.

The data collected for this study, including patient demographic data, treatment variables, and survey responses will be recorded by the research team in a secure password-protected database.

Data collected for this study will be entered into and managed via a secure REDCap Database. REDCap, Research Electronic Data Capture, is an open source platform that allows for the collection of research data in a secure manner over a web based interface. Usage of the platform is contingent on an open source license. The platform was developed by Vanderbilt University which MSK has a standing agreement with to allow the usage of REDCap for academic/research purposes.

For this protocol, electronic data entry forms may be completed online by study staff. [If applicable], electronic participant responses will also be collected either by sending participants a direct link or having the participants fill out the electronic survey on site.

Data will be housed in the Memorial Sloan Kettering Cancer Center's (MSKCC) Jersey data center. REDCap has been approved by MSKCC's Information Security to store PHI. The MSKCC Information Systems group is responsible for applying all operating system patches and security updates to the REDCap servers. All connections to REDCap utilize encrypted (SSL-based) connections to ensure data is protected. The server is backed up nightly in the event that disaster recovery would be necessary, and the system would need to be rolled back. Members of the Clinical Research Administration supporting the REDCap software will have access to REDCap projects for the purpose to ensuring the proper functioning of the database and the overall software system.

Permissions to the database for both internal and external users will be managed by the REDCap project manager or study staff. User access to the data is contingent on those a part of the study team and data sharing agreements in place with third party entities if applicable. Project managers are responsible for regularly auditing these permissions to ensure changes in staff are reflected appropriately.

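### The reason given for not blinding covers patients only, and nothing in the plan keeps the allocation from staff who settle outside emergency visits, unplanned clinic visits and chart-identified adverse events

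*Combined protocol and SAP*

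**What the plan says.** - **Blinding.** Section 12.3 (Randomization) states: "The trial will not be blinded, as it relies on patient knowledge". It gives no reason relating to staff.
- **Extraction.** Section 4.3, under Patient-centered outcomes, has urgent care visits, readmissions and symptom-triggered interventions collected from platform triggers and also "through thorough chart extraction by the clinical research coordinator (CRC) for 30 days after surgery".
- **Outside care.** The Study outcomes table lists, for emergency visits and admissions elsewhere, "Patient self-reporting via Patient Portal and corroborating phone call to patient by study team", together with the institutional database. Section 11, under Data sources and data linkage plans, says instead that patients who report an outside emergency visit "are contacted by clinical staff for further details as a routine part of follow-up care".
- **Primary variable.** Section 11, under Power calculation, analyses the proportion of patients with at least one emergency visit not leading to admission within 30 days.
- **Bias discussion.** Section 11, under Reporting plan, says lack of blinding matters little for emergency visits, "as this is objectively measured and not susceptible to reporting bias". It then says "Performance bias by clinicians is, however, a concern" and considers the advice nurses might give. It does not mention the person who classifies outcomes.
- **Access rights.** Section 13.1 says: "Permissions to the database for both internal and external users will be managed by the REDCap project manager or study staff". It does not say who may see the allocation.

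**The concern.** Patients in this trial cannot be masked, and nurses may learn the arm from them. Neither fact prevents masking of the people who decide whether a recorded event counts. The team states in section 2.0 that it expects Enhanced Feedback to do better. Someone who holds that expectation and knows the arm could, without intending to, resolve doubtful cases in one direction.

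The admission question matters most. An outside attendance judged to have ended in admission drops out of the primary endpoint, and one judged not to have done so stays in. The other exposed items are secondary outcomes under SA1b: whether a clinic visit was unplanned, for which the plan gives no working definition, and whether the chart shows an adverse event.

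This point concerns how staff classify an event that has come to their attention. Whether patients report outside visits at all is a different question, and the plan already addresses it.

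**Working it through.** **1. Which items depend on staff judgement**

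| Item | Source in the plan | Exposure |
|---|---|---|
| Emergency visits at the centre | Institutional database, captured automatically | Little |
| Readmissions to the centre | Institutional database | Little |
| Nursing calls, internal referrals | Captured automatically; chart extraction added | Little |
| Outside emergency visits and admissions | Patient report, phone corroboration, health information exchange data unless the patient opts out | Yes, where phone corroboration settles the facts |
| Clinic visits counted as unplanned | Visit captured automatically; unplanned status read from the record | Yes |
| Adverse events | Surgical Secondary Events Database and medical record | Partly, where found from the record |

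**2. The plan's own figures**

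Inputs from section 11: 2,750 patients, control rate 4.1%, alpha 5%, two-sided P values. Allocation is 1:1 (section 4.2), so n = 1,375 per arm. With p1 = 0.041, p2 = p1 × (1 − relative risk reduction), d = p1 − p2 and p̄ = (p1 + p2)/2, the continuity-corrected power is

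Φ{[d − 1/n − 1.96 √(2p̄(1 − p̄)/n)] / √([p1(1 − p1) + p2(1 − p2)]/n)}.

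This gives 45.5%, 63.6% and 85.2% for reductions of 33%, 40% and 50%, against 45%, 64% and 85% in the plan. The 67% row gives about 99% against the stated 96%; nothing here depends on that row. Masking assessors changes neither sample size nor power.

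**3. Fragility at the threshold**

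Expected control events are 0.041 × 1,375 = 56.4, taken as 56. For a control and b Enhanced Feedback events, z = (a − b)/√[(a + b)(1 − (a + b)/2,750)].

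- b = 38: 18/√(94 × 0.9658) = 1.89, P = 0.059
- b = 37: 19/√(93 × 0.9662) = 2.00, P = 0.045
- b = 34: 22/√(90 × 0.9673) = 2.36, P = 0.018

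One event separates 37 from 38, and four added events take 34 to 38. Fisher's exact test moves the boundary by one event (36: P = 0.043; 37: P = 0.057). Any count endpoint behaves this way at its threshold.

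**4. Possible size, under assumed inputs**

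The documents give no share of outside visits and no error rate. Suppose there is no true effect, a share s of primary events occurs outside the centre, and a fraction m of those is wrongly not counted in the Enhanced Feedback arm only. Then p2 = 0.041 × (1 − s × m), and the two-sided rejection rate is

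Φ[(d − 1.96 se0)/se1] + Φ[(−d − 1.96 se0)/se1],

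with se0 the pooled and se1 the unpooled standard error, without continuity correction.

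| s | m | Events lost (56.4 × s × m) | Rejection rate |
|---|---|---|---|
| 10% | 20% | 1.1 | 5.1% |
| 10% | 50% | 2.8 | 5.9% |
| 30% | 20% | 3.4 | 6.3% |
| 30% | 50% | 8.5 | 13.5% |

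For the last row: p2 = 0.03485, d = 0.00615, se0 = 0.00729, se1 = 0.00728. The range runs from negligible to moderate, and every row assumes error in one direction.

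**5. Two pairs of statements that disagree**

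- The Study outcomes table gives the outside-visit contact to the study team. Data sources and data linkage plans gives it to clinical staff. Until this is settled, nobody can say who would need to be masked.
- Reporting plan says the primary endpoint is not open to reporting bias. The Sensitivity analyses section names reporting that differs between arms as part of the main threat to validity.

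**The case against.** Much of the case on the other side stands.

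- **Most of the primary endpoint may involve no judgement.** Visits and readmissions at the centre come from its database, and exchange data supplement outside care. A reader might infer that the coordinator judges the whole primary endpoint; the sources listed do not support that.
- **Nobody is said to know the arm.** A reader might infer that the coordinator or caller sees the allocation. The documents do not say so. The gap is that nothing in the text reviewed prevents it, and a few pages after section 13.1 were not available for this review.
- **Adverse event grading is not at issue.** Events follow an established grading system, no section makes the coordinator the grader, and section 11 analyses events as binary or count, not by grade. What remains is whether an event is identified from the record.
- **Errors could be found later.** It would be too strong to say that misclassification is beyond repair: source documents are kept, REDCap has an audit trail (section 13.1), and sample audits occur at least twice a year (section 13.2). None of these is described as masked, however, and a call to a patient is harder to revisit than a chart.
- **The sensitivity analysis helps.** Comparing visits at and outside the centre by arm might reveal uneven handling, and counting the excess events needed to lose significance is the same arithmetic as 34 to 38 above. But it is framed around unreported emergency visits. It does not test the admission split or any SA1b endpoint.

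**Conclusion.** The gap is real and narrow. The stated reason for not blinding does not reach outcome assessors, the discussion of bias omits them, and the text reviewed does not mask extraction, corroboration or classification. The exposure is confined to outside emergency visits and their admission status, unplanned clinic visits, and adverse events identified from the medical record.

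The effect on the primary endpoint is unknown and may be small. The rejection rates of 5.1% to 13.5% rest on assumed outside shares of 10% to 30% and assumed one-arm losses of 20% to 50%. A reader might take the 37 versus 38 comparison as evidence of bias or of its size; it is neither. The change is still worth making because it is cheap and leaves design, sample size and power untouched.

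**What to change.** 1. **Section 12.3.** State that patients and treating staff may know the allocation, but that those who extract charts, make the corroborating research call and classify the exposed events have no access to the allocation field. Set this through REDCap and CRDB user rights, with allocation handled by another existing team member or directly by the system.
2. **Call script.** Fix the questions (place, date, admitted or not), with none about portal content.
3. **Unmasking field.** Have the classifier record if and how the arm became apparent.
4. **Who calls.** Reconcile the Study outcomes table with Data sources and data linkage plans, so that the role to be masked is identified.
5. **Reporting plan.** Amend the claim about reporting bias to agree with the Sensitivity analyses section, and add a sentence on outcome assessors.

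The cost is a user-rights setting, a short script, one data field and minor text edits. No new staff are needed if an existing team member or the system handles allocation. The drawback is that masking will be incomplete: chart notes may mention alerts, and alert-driven nursing calls are handled differently by design in the two arms, so reading them can hint at the allocation.
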